 - For any participant not taking statin therapy due to statin intolerance, including those participants taking bempedoic acid or fibrate monotherapy, written confirmation will be required of both the participant and the Investigator stating that the participant is statin intolerant, aware of the benefit of statins to reduce the risk of a MACE, and aware that many other patients who are unable to tolerate a statin were actually able to tolerate a different statin or dose.

Note: Statin intolerance will be defined as intolerance due to an adverse safety effect that started or increased during statin therapy and resolved or improved when statin therapy was discontinued, resulting in an inability to tolerate either 1) two or more statins at any dose, or 2) one statin at any dose and either an unwillingness to attempt a second statin or advice by a physician not to attempt a second statin.²⁵

- o Bempedoic acid for at least 8 weeks in combination with a maximally tolerated statin prior to Screening (Visit 1); and/or
- A PCSK9-targeted therapy alone or in combination with other lipid-modifying therapy for at least 4 doses prior to Screening (Visit 1).

Note: Patients taking inclisiran must have received at least 2 stable doses prior to Screening.

Note: Approximately 70% of the participants enrolled into this study should be taking HIS. No more than approximately 10% of participants in this study will be completely statin intolerant. Documentation in the electronic case report form (eCRF) of the reason why a participant is unable to take HIS is required. HIS include atorvastatin 40 and 80 mg and rosuvastatin 20 and 40 mg.

5. Have a fasting serum LDL-C at Screening (Visit 1) \geq 70 mg/dL (\geq 1.8 mmol/L);

Note: For eligibility purposes, LDL-C at Screening (Visit 1) will be calculated using the Martin-Hopkins equation unless TG \geq 400 mg/dL (\geq 4.5 mmol/L) or LDL-C \leq 50 mg/dL (\leq 1.3 mmol/L); in both cases, LDL-C level will be measured directly by preparative ultracentrifugation, also referred to as beta quantification.²⁶

- 6. Have fasting TG <500 mg/dL (<5.7 mmol/L) at Screening (Visit 1); and
- 7. Have an estimated glomerular filtration rate (eGFR) ≥15 mL/min/1.73 m² calculated using the Chronic Kidney Disease Epidemiology Collaboration equation²⁷ at Screening (Visit 1).

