Clinically significant abnormal laboratory or other examination findings (eg, ECG) that are detected during the study or are present at the date of the first dose of study treatment and significantly worsen during the study should be reported as AEs, as described below. The Investigator will exercise his or her medical and scientific judgment in deciding whether an abnormal laboratory finding or other abnormal assessment is clinically significant. Clinically significant abnormal laboratory values occurring during the study will be followed until repeat tests return to normal, stabilize, or are no longer clinically significant. Abnormal test results that are determined to be an error should not be reported as an AE. Laboratory abnormalities or other abnormal clinical findings (eg, ECG abnormalities) should be reported as an AE if any of the following are applicable:

- If an intervention is required as a result of the abnormality;
- If action taken with a study drug is required as a result of the abnormality; or

• Based on the clinical judgment of the Investigator.

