8.1.4 Events of Special Interest

ESIs will be monitored, regardless of whether these events were reported as AEs. Any events that qualify as an AE or SAE will be reported accordingly (see Sections 8.1, 8.2, and 8.3).

ESIs will include the following hepatic abnormalities, muscle-related abnormalities, new-onset diabetes mellitus (NODM) and/or hyperglycemia, renal abnormalities, changes to antihypertensive medication(s) due to changes in blood pressure, and ophthalmic events (ie, macular degeneration), described as follows:

- AST or ALT > 3 × ULN;
- Total bilirubin >2 × ULN;
- CK >5 × ULN;
- NODM or worsening of glycemic control;

Note: NODM is defined by 1 or more of the following criteria, based upon information from AE, medication, and laboratory data:

- o AE indicating new type 1 or type 2 diabetes;
- o Initiation of anti-diabetes medication with confirmation of the diagnosis of diabetes by blinded external review by experts in diabetology;

- o HbA1c \geq 6.5% (\geq 0.065 hemoglobin fraction); and/or
- Two consecutive values of fasting plasma glucose that are \geq 126 mg/dL (\geq 7.0 mmol/L).

Note: Worsening of glycemic control will be defined as an HbA1c increase from baseline >0.5% (>0.005 hemoglobin fraction) and/or a new concomitant medication or increase in current antidiabetic therapy in a participant with a baseline HbA1c $\ge 6.5\%$ (≥ 0.065 hemoglobin fraction).

- A >25% decrease in eGFR from baseline or an eGFR <15 mL/min/1.73 m², calculated using the Chronic Kidney Disease Epidemiology Collaboration equation, and/or an increase in serum creatinine of ≥0.3 mg/dL (≥26.5 μmol/L) from baseline;
- Changes to antihypertensive medication(s) due to changes in blood pressure in those
 participants receiving antihypertensive medication(s) treatment at baseline, and new
 antihypertensive medication prescriptions for participants not previously treated for
 hypertension; and
- Macular degeneration.

These ESIs will be monitored through review of the AE and laboratory databases.

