8.1.4.4 Guidelines for monitoring and management of significant changes in renal function

If at any time after Randomization (Visit 2 [Day 1]) a participant experiences ANY of the following, the participant will undergo a repeat confirmatory assessment as soon as is reasonably possible, preferably within 3 to 7 days of the laboratory result becoming available:

- A >25% decrease in eGFR from baseline, calculated using the Chronic Kidney Disease Epidemiology Collaboration equation;
- An eGFR <15 mL/min/1.73 m², calculated using the Chronic Kidney Disease Epidemiology Collaboration equation; and/or
- An increase in serum creatinine of ≥ 0.3 mg/dL (≥ 26.5 µmol/L) from baseline.

In consultation with the Medical Monitor and/or nephrologist, if no alternative etiology is determined, the study drug should be discontinued if participants experience an unexplained, confirmed increase in serum creatinine of ≥ 0.3 mg/dL (≥ 26.5 µmol/L) from baseline or an unexplained, confirmed $\geq 25\%$ decrease in eGFR from baseline.

If any of these individual laboratory parameters are confirmed, such events of decline in renal function should be recorded as an ESI.

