3.5.2 Event of Special Interest

Events of special interest (ESIs) include the following: hepatic abnormalities, muscle-related abnormalities, new-onset diabetes mellitus (NODM) and/or hyperglycemia, renal abnormalities, changes to antihypertensive medication(s) due to changes in blood pressure, and macular degeneration described as follows:

- AST or ALT > 3×ULN;
- Total bilirubin > 2×ULN;
- Creatine kinase (CK) > 5 × ULN;
- NODM or worsening of glycemic control;

Note: NODM is defined by 1 or more of the following criteria, based upon information from AE, medication, and laboratory data:

- AE indicating new type 1 or type 2 diabetes;
- Initiation of anti-diabetes medication with confirmation of the diagnosis of diabetes by blinded external review by experts in diabetology;
- HbA1c ≥6.5% (≥0.065 hemoglobin fraction); and/or
- Two consecutive values of fasting plasma glucose that are ≥126 mg/dL (≥7.0 mmol/L).

Note: Worsening of glycemic control will be defined as HbA1c increase from baseline >0.5% (>0.005 hemoglobin fraction) and/or a new concomitant medication or increase in current antidiabetic therapy in a participant with a baseline HbA1c \ge 6.5% (\ge 0.065 hemoglobin fraction)

- A >25% decrease in eGFR from Baseline or an eGFR<30mL/min/1.73 m², calculated using the Chronic Kidney Disease Epidemiology Collaboration equation, and/or an increase in serum creatinine of ≥0.3 mg/dL (≥26.5 µmol/L) from baseline;
- Changes to antihypertensive medication(s) due to changes in blood pressure in those participants receiving antihypertensive medication(s) treatment at baseline, and new

antihypertensive medication prescriptions for participants not previously treated for hypertension; and

Macular degeneration.

Values and changes from baseline will be summarized for ALT, AST, and total bilirubin by visit and treatment group. The number and percent of participants with abnormal values for ALT, AST, and total bilirubin will be summarized. These summaries of participants with abnormal values will be performed overall; by normal Baseline; and by abnormal Baseline for ALT, AST, and total bilirubin individually.

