Values and changes from baseline will be summarized for CK levels by visit and treatment group and visit. In addition, the number and percent of participants with abnormal CK values will be summarized. These summaries of participants with abnormal CK values will be performed overall, by normal Baseline CK, and by abnormal Baseline CK. Values of CK from Baseline to EOT will be summarized by treatment group and by Baseline eGFR category.

Cases of NODM will be recorded and summarized using the appropriate system organ class. These events will be summarized by severity and relationship to study drug for each treatment group.

Baseline eGFR will be summarized by treatment group for actual value and for baseline eGFR categories. Shift tables of eGFR category from baseline to EOT will be provided by treatment group. Shift tables of urine albumin-creatinine ratio from baseline to EOT will be provided by treatment group.

Participants will be identified as those who have a diagnosis of hypertension in their medical history and received antihypertensive medication(s) at Baseline. If a participant has an adverse event related to hypertension after Baseline (see Appendix B for preferred terms) and has any change in antihypertension medication within 30 days of the start date of the adverse event, that change in antihypertension medication will be considered due to a change in blood pressure. Participants will be identified as those who did not have a prior diagnosis of hypertension in their medical history but had an adverse event of hypertension (see Appendix B) after Baseline. If participants had an adverse event of hypertension and had initiation of antihypertension medication within 30 days of the start date of the adverse event, that initiation of an antihypertension medication will be considered due to a change in blood pressure.

The number and percentage of participants receiving/not receiving antihypertensive medication(s) at Baseline with changes to or initiation of new antihypertensive medication(s) due to changes in blood pressure will be summarized by treatment group.

Cases of macular degeneration will be recorded and summarized using the appropriate system organ class. These events will be summarized by severity and relationship to study drug for each treatment group.

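### SAP 3.5.2 conflicts with the protocol on the renal ESI limit (eGFR <30 against <15), and its blood-pressure derivation does not match the ESI definition and count table it serves

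*SAP*

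**What the plan says.** **Renal.** Protocol 8.1.4 lists as an ESI a more than 25% "decrease in eGFR from baseline or an eGFR <15 mL/min/1.73" m², and/or a creatinine rise of at least 0.3 mg/dL. Protocol 8.1.4.4 repeats the limit of 15 and says that, once confirmed, "such events of decline in renal function should be recorded as an ESI". SAP 3.5.2 gives the same three criteria with one number changed: "decrease in eGFR from Baseline or an eGFR<30mL/min/1.73" m². Inclusion criterion 7 (Protocol 4.1) reads "Have an estimated glomerular filtration rate (eGFR) ≥15 mL/min/1.73" m² at Screening. For output, SAP 3.5.2 plans a baseline eGFR summary by arm, and then: "Shift tables of eGFR category from baseline to EOT will be provided by treatment group". It names no count of renal ESIs. SAP section 5 declares one change from the protocol, the subgroup analysis.

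**Blood pressure.** The ESI item in SAP 3.5.2 repeats Protocol 8.1.4. It has two limbs: drug changes attributed to blood pressure in those on antihypertensives at baseline, and new prescriptions in those never treated for hypertension before. SAP 3.5.2 ends with a number-and-percentage table by arm, split by whether the participant was on antihypertensives at baseline and limited to changes or starts attributed to blood pressure.

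Between the two stands a derivation. Its first group needs a hypertension diagnosis and treatment at baseline. A drug change within 30 days of the start of a hypertension-related adverse event (AE), with terms from SAP Appendix B, is then attributed to blood pressure. Its second group needs no prior diagnosis, a hypertension AE, and a drug started within 30 days.

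**The concern.** A safety event should have one definition across protocol and SAP, and the rule that fills a table should select the people the table describes. Neither holds here.

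For the kidney, sites record ESIs against one limit while the SAP states another. Because the entry limit lies below the SAP limit, the SAP definition can be met on Day 1, although the protocol describes these events as a decline.

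For blood pressure, the table is labelled by treatment status and states no direction, but the rule feeding it works by diagnosis and looks almost entirely for raised pressure. A reader would take the percentages as covering all blood-pressure-driven drug changes. At stake is the meaning of a descriptive safety table, not the efficacy result, alpha or power.

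**Working it through.** **1. Renal: where the rules part.** Inputs: a fall of more than 25% (both documents); absolute limit 15 (Protocol 8.1.4 and 8.1.4.4) or 30 (SAP 3.5.2); entry from 15 (Protocol 4.1). With baseline eGFR b, a later value is an event on eGFR alone if

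- protocol: value < max(0.75b, 15)
- SAP: value < max(0.75b, 30)

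The thresholds coincide once 0.75b ≥ 30, that is b ≥ 30/0.75 = 40. Below that they differ:

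| b | Protocol event | SAP event |
|---|---|---|
| 25 | below 18.75 | below 30: already met at baseline |
| 30 | below 22.5 | below 30: any fall |
| 36 | below 27 | below 30: a fall of more than 6/36 = 16.7% |
| 40 | below 30 | below 30 |

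The creatinine criterion is the same in both documents. It may catch some falling cases under either, but never a stable one, so the clear difference is the participant stable at 15 to <30.

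Size: the documents give no eGFR distribution. Assuming 1% to 5% of 400 are stable in that range, 4 to 20 participants (1 to 5 per arm) would be flagged without decline if the definition is programmed. From the outputs actually named, the number is 0.

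**2. Blood pressure: definition, rule and table side by side.**

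| | Classifies by | Event |
|---|---|---|
| Definition (both documents) | antihypertensive treatment | change attributed to blood pressure, no direction stated; or a new prescription |
| Derivation (SAP 3.5.2) | hypertension diagnosis, plus treatment in the first group | Appendix B AE with a drug change or start within 30 days |
| Table (SAP 3.5.2) | treatment at baseline | change or start attributed to blood pressure, no direction stated |

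**3. Direction.** Appendix B has 23 terms: 17 raised or uncontrolled, 6 direction-neutral (five for abnormal pressure, one for labile pressure) and 0 low. The SAP gives no other route by which a change is attributed to blood pressure. A drug change in a treated participant that is tied to an AE coded as hypotension is therefore not counted.

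Size, on assumed shares: 50% to 80% of 400 treated at baseline, of whom 1% to 3% have a drug changed for low pressure.

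- Low: 400 × 0.50 × 0.01 = 2, or 0.5 per arm
- High: 400 × 0.80 × 0.03 = 9.6, or 2.4 per arm

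This is an upper estimate: some such AEs may be coded to a neutral term, and some changes may have no AE at all. With 50 to 80 treated per arm, one participant moves the percentage by 1/80 = 1.25 to 1/50 = 2 points.

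**4. Diagnosis.** The sentences attributing a change to blood pressure can be read as applying only to the group just named, or to everyone:

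| Diagnosed | Treated at baseline | Group-specific reading | General reading |
|---|---|---|---|
| yes | yes | change with listed AE | same |
| yes | no | in neither group | start with listed AE |
| no | yes | start only, with listed AE | change or start with listed AE |
| no | no | start with listed AE | same |

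Size of the second row on the group-specific reading, assuming 2% to 10% of 400 are diagnosed but untreated and 5% to 20% of them start a drug for blood pressure in about 16 weeks: 400 × 0.02 × 0.05 = 0.4 to 400 × 0.10 × 0.20 = 8 starts, or 0.1 to 2 per arm. This is a ceiling on what the diagnosis condition costs, because starts without a listed AE go uncounted on either reading. On the general reading the diagnosis condition costs 0 in this row. Some of these people were treated before and lie outside the definition's second limb anyway. With 20 to 50 untreated per arm, one participant moves that percentage by 1/50 = 2 to 1/20 = 5 points.

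**The case against.** The strongest reply is that little reported output changes. No specified renal table uses the limit of 30. The safety analysis is descriptive (SAP 3.5). Concomitant medications and vital signs are listed by subject (SAP 3.3.6 and 3.5.4), and SAP section 6 promises listings of all available data, so a reader can link drug, pressure and AE by hand. All of this stands and limits the harm. It does not make two different limits agree, or make the table match its label.

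A second reply is that an AE-plus-30-day link is a workable rule, since the documents do not show that the reason for a drug change is collected. That is fair. A reader might infer that tying the ESI to an AE breaks the protocol, because "ESIs will be monitored, regardless of whether these events were reported as AEs". The protocol is mixed, however. It also says "These ESIs will be monitored through review of the AE and laboratory databases", and Protocol 8.1 asks for an abnormal finding to be reported as an AE "If an intervention is required as a result of the abnormality". The link itself is defensible; what does not fit is the one-sided term list under a label with no direction.

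A third reply is that SAP section 5 covers changes to protocol-specified analyses, and Protocol 9.2.2 specifies no ESI analysis. Silence there about the blood-pressure derivation is therefore not clearly an undeclared deviation. That stands. The renal limit is different: it is a changed number in a definition that the protocol states twice.

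**Conclusion.** The point holds as a mismatch to be corrected before unblinding. It does not threaten the trial's conclusions.

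Certain from the text: the renal limits contradict each other without declaration, the eGFR rules differ only for baseline values below 40, and the SAP limit can be met at entry. Also certain is that the blood-pressure rule classifies by diagnosis where the table classifies by treatment, and that its term list has nothing for low pressure. The step from that list to uncounted drug changes assumes that the table is programmed from the derivation as written.

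Stronger readings that the documents do not support:

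- That the limit of 30 alters reported renal results. It does so only if a flag or count is added.
- That the SAP redefines the blood-pressure ESI. Its definition repeats the protocol; only the derivation departs from it.
- That the protocol expressly asks for changes in both directions. It states no direction, and the low-pressure argument bears only on participants treated at baseline.
- That diagnosed but untreated participants are certainly dropped. That depends on one of two readings which the text does not settle.

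The documents give no counts. On the assumed shares, probably a few participants per arm at most are affected.

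**What to change.** **Renal.** Reconcile the eGFR limit between Protocol 8.1.4 and SAP 3.5.2, or declare and justify the difference in SAP section 5. Which limit is right is not for this review to say. If a renal ESI count is produced, show participants already below the limit at baseline separately.

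**Blood pressure.** In the SAP 3.5.2 derivation, classify participants by antihypertensive treatment at baseline, as the table does, and not by diagnosis. Then either add hypotension and decreased-pressure preferred terms to Appendix B and reword the AE trigger to match, or keep the list and relabel the table as changes associated with hypertension AEs. Reconcile the definition's second limb, which turns on any earlier treatment for hypertension, with the table row, which turns on treatment at baseline.

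**Cost.** SAP rewording and some reprogramming, to be done before unblinding so that the rule stays pre-specified.

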8.1.3 Assessment of Adverse Events by the Investigator

The Investigator will assess the severity (intensity) of each AE as mild, moderate, or severe, and will also categorize each AE as to its potential relationship to the study drugs using the categories of yes or no.

Assessment of severity

Mild – An event that is easily tolerated and generally not interfering with normal daily activities.

Moderate – An event that is sufficiently discomforting to interfere with normal daily activities.

Severe – An event that is incapacitating with inability to work or perform normal daily activities.

Causality assessment

The relationship of an AE to the administration of the study drugs is to be assessed according to the following definitions:

No (unrelated, not related, unlikely to be related) – The time course between the administration of study drugs and the occurrence or worsening of the AE is not consistent with a causal relationship and another cause (concomitant drugs, therapies, complications, etc) is suspected.

Yes (possibly, probably, or definitely related) – The time course between the administration of study drugs and the occurrence or worsening of the AE is consistent with a causal relationship and no other cause (concomitant drugs, therapies, complications, etc) can be identified.

The definition implies a reasonable possibility of a causal relationship between the event and the study drugs. This means that there are facts (evidence) or arguments to suggest a causal relationship.

The following factors should also be considered:

• The temporal sequence from a study drug administration-

The event should occur after a study drug is given. The length of time from study drug exposure to event should be evaluated in the clinical context of the event.

• Underlying, concomitant, intercurrent diseases-

Each report should be evaluated in the context of the natural history and course of the disease being treated and any other disease the participant may have.

Concomitant drug-

The other drugs the participant is taking or the treatment the participant receives should be examined to determine whether any of them might be recognized to cause the event in question.

• Known response pattern for this class of study drug-

Clinical and/or preclinical data displayed in the Investigator's Brochure may indicate whether a particular response is likely to be a class effect.

• Exposure to physical and/or mental stresses-

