3.5.1 Adverse Events (AEs)

AEs will be categorized by primary system organ class and preferred term as coded using the current MedDRA version category designation.

An overview of treatment-emergent AEs (TEAEs) will be provided including counts and percentages of participants with the following:

- Any TEAEs (overall and by maximum severity)
- Any TEAEs (non-serious)
- Any study drug related TEAEs (overall and by maximum severity)
- Any TEAEs leading to discontinuation of study drug
- Any drug related TEAEs leading to discontinuation of study drug
- Any treatment-emergent serious AEs (TESAEs)
- Any study drug related TESAEs
- Any TEAEs leading to death.

The TEAEs described above will be summarized separately by system organ class and preferred term. The non-serious TEAEs occurring in more than 2% of participants in any treatment group and preferred term will be summarized.

Listings will be presented specifically for TEAEs, TESAEs, TEAEs leading to discontinuation of study drug, and TEAEs leading to death.

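### SAP 3.5.2 specifies no participant-level count of new-onset diabetes met on laboratory or medication criteria without an AE, and no event-of-special-interest summary of worsening glycemic control

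*SAP*

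**What the plan says.** SAP 3.5.2 repeats the definition in Protocol 8.1.4: "NODM is defined by 1 or more of the following criteria, based upon information from AE, medication, and laboratory data". Any one of four criteria is enough:

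- an AE of new diabetes;
- a start of anti-diabetes medication, with the diagnosis confirmed by blinded external review;
- HbA1c at or above 6.5%;
- two consecutive fasting glucose values at or above 126 mg/dL.

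The companion event is defined from laboratory and medication data only: "Worsening of glycemic control will be defined as HbA1c increase from baseline >0.5% (>0.005 hemoglobin fraction"), and/or new or increased antidiabetic therapy, with a baseline HbA1c condition of at least 6.5%.

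Protocol 8.1.4 separates these events from AE reporting: "ESIs will be monitored, regardless of whether these events were reported as AEs".

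The only output specific to NODM is in SAP 3.5.2: "Cases of NODM will be recorded and summarized using the appropriate system organ class", followed by "These events will be summarized by severity and relationship to study drug for each treatment group". The section specifies no output for worsening of glycemic control.

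**The concern.** The definition draws on three data sources, but the display is described by attributes that belong mainly to one of them. A raised HbA1c or a repeated glucose value has no investigator-assessed severity or relationship to study drug. The SAP does not say how such a case would be given these attributes, or where it would be counted if it has none.

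At stake is what the glycemic safety table measures. If the programmer builds it from AE records, which is the natural reading of the display, it shows how often investigators reported a diabetes AE. That can differ from how often the defined event occurred. For worsening of glycemic control a reader would find no event rate at all, although the protocol made it an event of special interest and admits participants with existing diabetes.

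**Working it through.** No arithmetic settles this. The check is to trace each criterion to every planned safety output in SAP 3.5.1 to 3.5.3 and Protocol 9.2.2.

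**Where the display attributes come from.** Protocol 8.1.3 ties severity to AEs: "The Investigator will assess the severity (intensity) of each AE as mild, moderate, or severe". The same section has the investigator judge relationship for each AE. System organ class comes from dictionary coding; SAP 3.5.1 states "AEs will be categorized by primary system organ class and preferred term", and SAP 3.3.5 codes medical history the same way. Severity and relationship are therefore AE-only attributes in these documents. System organ class is not strictly so, but it is not assigned to laboratory values.

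**Trace by criterion.**

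| Criterion | Has severity and relationship? | Planned count of participants |
|---|---|---|
| NODM: AE of new diabetes | Yes | NODM summary and TEAE tables |
| NODM: medication start, externally confirmed | Only if also reported as an AE | None specified otherwise |
| NODM: HbA1c at or above 6.5% | Only if also reported as an AE | None specified otherwise |
| NODM: two fasting glucose values at or above 126 mg/dL | Only if also reported as an AE | None specified otherwise |
| Worsening: HbA1c rise above 0.5% | Only if also reported as an AE | No event summary |
| Worsening: new or increased therapy | Only if also reported as an AE | No event summary |

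**Whether another output fills the gap.** SAP 3.5.3 summarizes laboratory values and changes from baseline, gives shift tables for unnamed selected parameters by low, normal and high, and lists chemistry results. None of these applies the 6.5%, 126 mg/dL or 0.5% thresholds. The medication tables in SAP 3.3.6 are by drug class and preferred term and are not linked to a glycemic event.

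**Comparison within SAP 3.5.2.** Participants with abnormal ALT, AST, bilirubin or CK values are to be given as number and percent. So are participants with antihypertensive changes, under a derivation rule that combines AE and medication data. The NODM text instead has the same two-sentence form as the text for macular degeneration, an event with no laboratory or medication criterion.

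**Timing of HbA1c.** Protocol 8.7.1 schedules HbA1c at Screening, Day 84 and any EOT visit. AE collection runs to Day 112 (Protocol 8.1). Without an EOT visit, the only scheduled post-baseline HbA1c is at Day 84, nominally 112 − 84 = 28 days before AE collection ends. An untreated threshold crossing has little time to lead to an intervention that would make it an AE.

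**Who could meet the NODM thresholds.** Type 2 diabetes is a qualifying risk factor (Protocol 4.1), and HbA1c is exclusionary only at 10.0% or above (Protocol 4.2). The laboratory criteria for NODM do not exclude existing diabetes. A participant who enters with HbA1c between 6.5% and the 10.0% limit and stays there would satisfy the HbA1c criterion. A literal flag would therefore count prevalent disease as new onset.

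**The case against.** The best defence is that the SAP defines NODM to include laboratory and medication cases and then says that cases of NODM will be summarized. Read together, those cases are in scope. That is fair. A reader might infer that they are excluded and will not be counted, but the documents do not say so. They leave open how a case without an AE record is counted or classified.

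Second, many cases will also be AEs. Protocol 8.1 calls for an AE report when a laboratory abnormality requires intervention or action on study drug, or on the investigator's judgment. Treated NODM and treated worsening will often qualify and then appear in the TEAE tables. This narrows the gap mainly to untreated threshold crossings, which rest on judgment. Protocol 8.1.4.3 covers referral for newly diagnosed diabetes but does not require an AE or event record. Protocol 8.1.4.4, by contrast, does require confirmed renal changes to be recorded as events of special interest.

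Third, a reader might infer that worsening of glycemic control goes wholly unreported. It does not: HbA1c and glucose are summarized and listed, and treated cases can surface as AEs. What is missing is the count of the defined event.

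Fourth, a reader might infer a biased comparison between arms. Allocation and lipid results are blinded and safety is descriptive, and nothing in the documents points to reporting that differs by arm.

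Protocol 8.1.4 also closes with "These ESIs will be monitored through review of the AE and laboratory databases", which omits medication data. Since the same section names medication in the NODM definition, this is an editorial mismatch.

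**Conclusion.** The point holds as a gap in the specified safety output. For NODM, no participant-level count is specified for cases met on HbA1c, fasting glucose or medication without an AE. For worsening of glycemic control, no event summary is specified at all; that part follows directly from the text. The likely result is a glycemic display that follows AE reporting more closely than the defined event.

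The conclusion assumes that the display is built as SAP 3.5.2 describes it and that severity and relationship are available only from AE records, as Protocol 8.1.3 indicates. The documents give no expected rate of threshold crossings and no expected fraction reported as AEs, so the number of uncounted cases cannot be stated. An undercount is likely but not certain. No efficacy analysis or error rate is affected. It is worth correcting because the event was singled out in advance and the data are already collected.

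**What to change.** In SAP 3.5.2, derive participant-level flags from AE, concomitant-medication and laboratory data, and tabulate n (%) per arm for:

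- **NODM**, overall and by criterion met, including the outcome of the blinded external review for the medication criterion. Limit the denominator to participants without diabetes at baseline, judged from medical history, anti-diabetes medication or baseline HbA1c or glucose. Without this limit the table would mix prevalent with new disease.
- **Worsening of glycemic control**, overall and by component (HbA1c rise; new or increased therapy). State the denominator, and say whether the baseline HbA1c condition applies to both components or only to the therapy component, since the sentence can be read either way.

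Keep the severity and relationship summary as a secondary display, labelled as covering AE-reported cases. Add concomitant-medication data to the sources named at the end of Protocol 8.1.4, so that it agrees with the definition above it.

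The cost is SAP wording and one extra derived table, with no new data collection. Reported event counts may rise.
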